7.4 Evaluation of pharmacodynamics

The analysis of PD data and parameters are beyond the scope of this SAP. Separate analysis plans may be developed for these analyses. In this SAP only listing of the following PD parameters is planned:

- Fecal calproteïn.
- wr-CRP
- delayed type hypersensitivity skin testing

8. Evaluation of Safety

All analysis of safety will be performed using the Safety Analysis Set.

Results of all safety assessments, including physical examinations, body weight, vital sign determinations, AE monitoring, ECGs, and clinical laboratory evaluations, will be summarized with descriptive statistics by dose Cohort and overall, and/or presented in data listings.

8.1 Adverse events

The onset date of an adverse event will be compared to the date of investigational product dosing to determine if the adverse event is treatment-emergent or not. Adverse events with an onset date on or after the first date of investigational product dosing will be classified as treatment emergent adverse events (TEAEs). If the adverse event onset date is missing or partial, the date will be compared as far as possible with the date of investigational product dosing. Adverse events will be assumed to be TEAEs unless there is clear evidence (through comparison of partial dates) to suggest that the adverse event started prior to receiving the dose of investigational product.

TEAE will be summarized in a table that presents the number and percentage of subjects with any TEAE, with any serious TEAE, with any drug-related TEAE, with any TEAE leading to discontinuation and death overall and within each treatment period (Double-Blind Induction Therapy Period, LTE Therapy Period, and OLE Therapy Period) by treatments (each KHK4083 dose level versus placebo). It will also include the total number of adverse events in each of these categories. All TEAEs will be summarized showing the number and percentage of subjects for each event with a start time within the treatment period (i.e., Double-Blind Induction Therapy Period, LTE Therapy Period, and OLE Therapy Period) and by treatments (each KHK4083 dose level versus placebo) during Induction Therapy or KHK4083 dose level versus placebo during OLE /LTE Therapy Period. All TEAEs will be summarized by SOC and Preferred Term as well as by Preferred Term in decreasing frequency. Two additional summary tables are presented for serious TEAEs and Related TEAEs.

	Forms			
	Title	Statistical Analysis Plan Template		
	Code	Version	Effective Date	Page
	FRM_ST03_032	01	23 Apr 2015	35 of 53

Listings of all adverse events (including non-treatment-emergent events) will be provided. This listing will be presented by dose cohort and will include site-subject identifier, adverse event (SOC, Preferred Term, reported term), start date, stop date, study day, severity grade, seriousness, relationship to drug, action taken with study treatment, and outcome. Also SAEs will be listed in a similar format as described above. Deaths which are adverse events leading to death, adverse events leading to discontinuation and adverse events with withdrawal of investigational product also will be listed in the same manner.

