9.2 Baseline Visit (Week 0, Day 1)

Before administration of KHK4083 or placebo, the subject's eligibility criteria (Inclusion/Exclusion Criteria) and results of Screening assessments must be reviewed by the Investigator (his/her designee) to ensure that the subject is qualified to be randomized in the study. A partial Mayo Clinic score (without sigmoidoscopy) including the Physician's Global Assessment, which is to be performed after review of all available clinical data, will be recorded at Baseline. A total Mayo clinical score will be evaluated at Baseline, using subject

diary entries within the 10 days prior to Baseline, combined with the sigmoidoscopy results prior to Baseline and the Physician's Global Assessment. Diary entries for the three qualifying days closest to Baseline will be used for this evaluation but the entries do not have to be made on consecutive days. A total Mayo score of 4-10 and endoscopy subscore (mMES determined by a central reader) of at least 2 are required as per the Inclusion Criteria (refer to Inclusion Criteria #5)

The sigmoidoscopy results from the central reader are required before a subject is randomized in the study (*Note: A sigmoidoscopy with biopsy, for mMES, UCEIS, modified Baron score and total Mayo Clinic score, is to be performed before randomization and within 7 to 28 days prior to the first dose; an mMES of at least 2 is required. For subjects who are rescreened, the original screening sigmoidoscopy can be used to satisfy the entry criteria if obtained within 42 days prior to the first dose.*)

An IBDQ will be administered as a quality-of-life assessment at Baseline.

The following will be collected at Baseline (Day 1) (refer to Table 9-1 for the schedule of study events at Baseline).

- Complete physical examination (Section 10.6.4);
- Vital signs (systolic and diastolic blood pressure, radial pulse, and respiration rate) and body temperature (oral) (Section 10.6.2);
- Body weight (Section 10.6.4);
- 12-lead ECG (Section 10.6.3);
- Adverse events (pre-treatment and on-site post-infusion monitoring is required for at least 3 hours after the first dose as well as a phone call at approximately 48 to 72 hours post-infusion for any subject who does not return for the scheduled visit at the investigative site) (Section 10.6.5);
- Concomitant medications (Section 8.5);

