10.6.7 Adverse Event and Serious Adverse Event Reporting

The description of each AE will identify the subject, date of onset, the date of resolution, the severity of the event, the action taken regarding the AE and the investigational product (KHK4083 or placebo), the outcome of the event, and the relationship of the event to KHK4083 or placebo. A medical condition present at Screening, but that has increased in frequency or severity, must be recorded as an AE. For screen failures, SAEs should be collected and recorded only until the subject is determined to be a screen failure. Screening or withdraws consent to participate in the study, except for SAEs that occur outside of that window which are attributed to screening-specific procedures. All AEs with onset after signing of the ICF should be collected. Adverse events which occur prior to first administration of investigational product should be identified as occurring pretreatment. No AE data should be entered on the eCRF for screen failures.

Standard medical terminology should be used to document AEs. The subject's exact description of the event will be recorded in the source documentation. In the case of signs and symptoms, the underlying illness or diagnosis will be recorded as the event when known. For SAEs, a single term for the diagnosis or underlying illness should be provided on the SAE Report form; if the underlying illness/diagnosis is unknown, the chief sign/symptom making the event serious should be recorded. Suspected Unexpected Serious Adverse Reactions (SUSARs) will be collected and reported according to regulatory guidelines.

All serious and non-serious AEs must be followed for a final outcome until the end of the Post-treatment Follow-up Period. An outcome of "unknown" is not considered to be an acceptable final outcome. An outcome of "not resolved" is an acceptable final outcome for non-serious AEs at the end of a subject's participation in a study, and for SAEs at database lock.

All SAEs require expeditious handling to comply with regulatory requirements. **Any SAE occurring in a clinical study subject must be reported to the Sponsor or designee within 24 hours of the Investigator having knowledge of the SAE.**

The Investigator or other qualified individual at the investigative site must complete the SAE Report form and e-mail it to the Sponsor or designee. All telephone communication regarding an SAE must be followed by a written report.

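### SAP 8.1 defines treatment-emergent by calendar date alone, so an adverse event that began on Day 1 before the first infusion is counted as a TEAE

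*SAP*

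**What the plan says.** SAP 8.1 compares the onset date of each adverse event with the date of dosing. It treats as TEAEs all "Adverse events with an onset date on or after the first date of investigational product dosing". Where the onset date is missing or partial, the event is assumed to be a TEAE "unless there is clear evidence (through comparison of partial dates) to suggest that the adverse event started prior to receiving the dose". The same section then tabulates "each event with a start time within the treatment period", by period and treatment.

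Protocol 10.6.7 draws the line at the administration itself: "Adverse events which occur prior to first administration of investigational product should be identified as occurring pretreatment". Collection begins at consent ("All AEs with onset after signing of the ICF should be collected"), so events on the morning of Day 1 are within scope. The Day 1 list in protocol 9.2 includes "Adverse events (pre-treatment and on-site post-infusion monitoring is required for at least 3 hours after the first dose".

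SAP 9.6 plans Listing 16.2.7-1 for pre-treatment adverse events. The SAP does not say how an event qualifies for it.

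**The concern.** The protocol and the SAP place the boundary differently. For a subject with an event a few hours before the first infusion, the site is asked to mark it as pretreatment, while the SAP rule, which looks only at the date, puts it in the TEAE tables. Such an event cannot have been caused by the drug.

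The number and percentage of subjects with adverse events is one of the measures of safety and tolerability (protocol 10.1.2), and safety and tolerability is the primary objective of Part A. The groups are small, so a single event can be visible in a percentage. Without a stated definition for Listing 16.2.7-1, one event could also be listed as pretreatment and counted as treatment-emergent, or the site's identification could be ignored in both outputs.

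**Working it through.** The plan states no figure for this point. The check is a comparison of texts, followed by a simple scale calculation.

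**1. Does any SAP text separate pre-dose from post-dose on Day 1?**

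- *Main rule (SAP 8.1).* It uses the onset date only. Every event dated Day 1 passes.
- *Exception (SAP 8.1).* It follows the sentence on missing or partial dates and relies on comparing partial dates. A complete Day 1 date equals the dosing date, so the comparison cannot show that the event came first.
- *Reference to start time (SAP 8.1).* This allocates TEAEs to a treatment period. It does not redefine which events are TEAEs.
- *Study day (SAP 4.1).* For an event on the dosing date, study day = event date − first dosing date + 1 = 0 + 1 = 1. Pre-dose and post-dose events both receive Day 1. The adverse event listing carries start date and study day but no clock time, so those columns would not show the difference.
- *Baseline (SAP 4.1).* Baseline is the last value before administration on Day 1. For measurements, the SAP does use the dose and not the date as the boundary.

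A fully dated Day 1 pre-dose event is therefore a TEAE under SAP 8.1 and is to be identified as pretreatment under protocol 10.6.7.

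**2. What data could separate them?**

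- Infusion start time is recorded (SAP 6.1).
- The protocol's general description of an adverse event asks for the date of onset (10.6.7). Timing relative to administration is required only for infusion reactions (10.6.7.1).
- The site's pretreatment identification is therefore the main workable basis, with onset time as a supplement where one exists.

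**3. Size of one misclassified subject.**

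Planned group sizes are 9 at each dose level not taken into Part B, 27 at the recommended dose and 15 on placebo (protocol 8.1.4.1 and 12.3.4): 9 + 9 + 27 + 15 = 60. If a subject's only TEAE is a Day 1 pre-dose event, the rate of subjects with any TEAE rises by 100/n percentage points:

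| Group | n | Shift |
|---|---|---|
| Dose level in Part A | 9 | 100/9 = 11.1 |
| Pooled placebo | 15 | 100/15 = 6.7 |
| Recommended dose | 27 | 100/27 = 3.7 |
| All subjects | 60 | 100/60 = 1.7 |

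The same shift applies to a preferred-term row when this is the subject's only event of that term.

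**4. How likely is at least one affected subject?**

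The documents give no frequency. Taking an assumed per-subject probability p, the chance of at least one is 1 − (1 − p)^n and the expected number is np:

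| Assumed p | Expected among 60 | Chance of at least one among 60 | Chance in a 9-subject arm |
|---|---|---|---|
| 1% | 0.6 | 45% | 9% |
| 3% | 1.8 | 84% | 24% |
| 5% | 3.0 | 95% | 37% |
| 10% | 6.0 | 99.8% | 61% |

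These values of p illustrate a range. They are not estimates.

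**The case against.** The case for leaving the rule alone has several parts.

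- *The protocol sentence is a recording instruction.* Protocol 10.6.7 tells sites what to identify. Protocol 12.5, which covers the safety analysis, does not define a TEAE by clock time relative to the first infusion. A reader might infer that the SAP overrides a protocol analysis definition. It does not, because the protocol leaves that definition open. What remains is that the SAP makes no stated use of information that sites are asked to supply.
- *A date-only rule is a cautious convention.* With date-level data it over-counts and does not lose post-dose events. This stands, and it is a reason to keep the default for unresolved Day 1 events. It is no reason to count events known to precede drug.
- *Protocol 9.2 does not prove that same-day onsets occur.* Pre-treatment events collected at that visit may have begun during screening, and SAP 8.1 already excludes those by date. This is fair. The passage shows that such events would be collected, not how often they arise.
- *Other outputs limit the harm.* A pre-dose event should be judged not related and so drop out of the related-TEAE tables. Escalation and the Part B dose rest on Safety Monitoring Committee review under its own charter, and the unblinded 12-week tables come only after Part B induction is complete. This also stands: no trial decision can be shown to turn on the rule. The all-causality tables would still carry the event.

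**Conclusion.** The point holds as a minor error in a stated rule. SAP 8.1 counts as treatment-emergent a fully dated Day 1 event that began before the first infusion, and nothing else in the SAP corrects this. The effect is to inflate TEAE counts. The shift of 11.1, 6.7 or 3.7 points per affected subject is a ceiling. It assumes the planned group sizes, and it applies to the any-TEAE rate only if the subject has no other TEAE, or to a term row only if the subject has no other event of that term.

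Three stronger readings are not supported:

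- *That the rule favours one arm.* Assignment is randomized and blinded, so the error should be similar across arms in expectation.
- *That TEAE incidence by dose is the primary safety output of Part A.* Protocol 10.1.2 lists adverse events alongside physical examination, vital signs, body weight, ECG and laboratory findings.
- *That a pretreatment flag is certainly in the database.* The protocol asks for the identification, but the documents do not show the eCRF or describe such a field.

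**What to change.** Add to SAP 8.1:

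- An event with onset on Day 1 is not a TEAE if the site identified it as pretreatment under protocol 10.6.7, or if a recorded onset time exists and precedes the start of the first infusion.
- All other Day 1 events remain TEAEs by default.
- Listing 16.2.7-1 uses the same definition, so that no event appears both there and in the TEAE tables.

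The cost is a few lines of SAP text and a small change to the derivation of the TEAE variable. The downside is dependence on the pretreatment identification being captured. Confirm this against the eCRF before the SAP is amended. If it is not captured, only events with a recorded onset time can be reclassified, and the SAP should state that the remaining Day 1 events are counted as TEAEs because their order relative to the infusion is unknown.

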6.1.1 Induction Therapy: Week 0 to Week 12 (Last Dose at Week 10)

Double-blind Induction Therapy is separated into Part A for administration of multiple ascending IV doses of KHK4083 (or placebo) to subjects in Cohorts 1 - 3 and Part B for administration of the recommended IV dose (one of three dose levels identified in Part A) of KHK4083 (or placebo) to subjects in Cohort 4. Subjects in Part A are prohibited from participating in Part B.

Subjects in each cohort will be randomly assigned in a 3:1 ratio to receive KHK4083 or placebo by IV infusion over 60 minutes (\pm 10 minutes). Each subject will receive a total of 6 treatments (one IV infusion per treatment) every 2 weeks from Week 0 (Day 1) to Week 10 of Induction Therapy. Safety assessments (e.g., after 2 treatments for 1.0 mg/kg and 3 treatments for 3.0 and 10 mg/kg are administered and 14-day safety data from the last treatment are available) will determine whether dosing will continue for subjects within a cohort and if the investigational product will be administered at the next higher dose level for subjects in the next cohort in Part A or for Cohort 4 in Part B (refer to Section 6.3 for details on the Safety Monitoring Plan).

For subjects in all cohorts, a sigmoidoscopy with biopsy is scheduled at Week 12 to assess improvement in the mucosa from Baseline (Week 0) to Week 12. It is highly recommended that the sigmoidoscopy with biopsy be performed within 7 to 13 days prior to the Week 12 visit. The sigmoidoscopy results from the central reader are required before a subject receives treatment in the OLE/LTE Therapy phase.

6.1.2 Long-term Extension Therapy: Week 12 (First Dose) to Week 52

The LTE is only active for subjects who entered it prior to approval of Amendment 2. Subjects who sign an ICF under Amendment 2 are eligible for the OLE (see Section 6.1.3).

Subjects who completed double-blind Induction Therapy (i.e., at least five of six treatments) and had a clinical response or mucosal healing were eligible to continue in double-blind LTE Therapy. A clinical response is defined as a reduction in the total Mayo Clinic score of at least 3 points and a decrease of at least 30% from Baseline (Week 0) to Week 12, and a reduction in the rectal bleeding subscale of at least 1 point from Baseline (Week 0) to Week 12 or an absolute rectal bleeding score of 0 or 1 at Week 12. Mucosal healing is defined as a mMES of 0 or 1.

All subjects who qualified were to have been given two options:

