8.1.5 Post-treatment Follow-up Period

Post-treatment Follow-up assessments will continue for 16 weeks after the last infusion associated with the subject's treatment period. For subjects who only receive Induction Therapy (i.e., last dose at Week 10 and do not continue in OLE/LTE Therapy), the Post-treatment Follow-up visits will be at Weeks 16, 20, and 26. For all subjects who receive both Induction Therapy and OLE/LTE Therapy (last dose at Week 48), the Post-treatment Follow-up visits will be at Weeks 56, 60, and 64. Subjects removed from the study for AEs will be followed until there is a return to the subject's baseline condition, or until a clinically satisfactory resolution is achieved. The date of the subject's last post-treatment study visit will be considered the End-of-Study date.

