4.1 General

General descriptive statistics for continuous variables include the n (number of observed values), the mean, standard deviation, median, minimum, and maximum values. For categorical variables, the number and percentage of subjects with a specific level of the variable will be presented. The percentage will be calculated using the subjects with a reported value. Counts of missing subjects will be identified for variables that had one or more subjects with a missing result. Descriptive statistics will be presented by treatment Cohort (KHK4083 dose levels; combined KHK4083; and placebo) and by visit.

Unless there are any notes, the following rules will be applied for all tables and figures;

- Data from placebo subjects in each Cohort will be combined, not depending on treatment period (Double-Blind Induction Therapy, Long-Term Extension Therapy, Open-Label Extension Therapy, or Follow-up).
- In the case that Screening or Baseline is necessary in the tables and figures related to LTE Therapy Period, OLE Therapy Period, or Follow-up Period, the data at Screening or Baseline will be used or displayed.
- Double-Blind Therapy Period will be defined as the period including both Double-Blind Induction Therapy Period and LTE Therapy Period.
- When “Week xx” (xx: number) is necessary, “Week xx” displayed on CRF will be used or displayed.

To explain how data are summarized, the figure showing the relationship between period and dose of Investigational Product is displayed in Figure 3 and the table defining the category is displayed in Table 2.

[figure not shown]
	Forms			
	Title	Statistical Analysis Plan Template		
	Code	Version	Effective Date	Page
	FRM_ST03_032	01	23 Apr 2015	20 of 53

Figure 3 Relationship between Period and Dose of Investigational Product

Subjects who do not move to OLE/LTE Therapy

Subjects who move to OLE/LTE Therapy

[figure not shown]

Table 2 Category in Tables and Figures

	4083 Randomized				Placebo Randomized			
	Cohort 1	Cohort 2	Cohort 3	Cohort 4	Cohort 1	Cohort 2	Cohort 3	Cohort 4
Summary Pattern	Category In Tables and Figures							
Double-Blind Induction Therapy Period	1.0 mg/kg	3.0 mg/kg	10 mg/kg	1.0, 3.0 or 10 mg/kg	Placebo			
Double-Blind Therapy Period ¹⁾								
Double-Blind Therapy Period and Double-Blind Therapy Follow-up Period ²⁾								
LTE Therapy Period								
LTE Therapy Period and Double-Blind Therapy Follow-up Period	1.0 mg/kg	3.0 mg/kg	10 mg/kg	1.0, 3.0 or 10 mg/kg	Placebo ³⁾			

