OLE Therapy Period								
OLE Therapy Period and OLE Therapy Follow-up Period								

1) Double-Blind Therapy Period includes both Double-Blind Induction Therapy Period and LTE Therapy Period.

2) Double-Blind Therapy Follow-up Period includes both Follow-up Periods after Double-Blind Therapy Period and LTE Therapy Period.

3) For subjects randomized to Placebo, they receive 4083 administration during the duration but they are summarized as one category as "Placebo".

Image which shows the relationship between summary pattern and data will be displayed in Figure 4.

Figure 4 Summary Patterns

Forms

Title Statistical Analysis Plan Template

Code

Version

Effective Date

[figure not shown]
Page

FRM_ST03_032

01

23 Apr 2015

21 of 53

General reporting conventions will include the following:

- The baseline value for any measurement is the last value obtained prior to receiving administration of KHK4083 or placebo on Day 1 at Week 0. All nominal time points will be used for analysis; actual assessment times will not be used to reclassify the time point at which a measure was taken.

	Forms			
	Title	Statistical Analysis Plan Template		
	Code	Version	Effective Date	Page
	FRM_ST03_032	01	23 Apr 2015	22 of 53

- Study day: Study day will be calculated relative to the date of KHK4083 or placebo administration (Day 1) as:
 - (If Date of event \geq Date of first investigational product administration) Date of event – Date of first investigational product administration + 1 and
 - (If Date of event $<$ Date of first investigational product administration) Date of event – Date of first investigational product administration

This formula will be used when calculating days to a specific event (i.e., concomitant medication and/or AE start date). A negative study day indicates an event prior to investigational product administration.

- Unless otherwise noted, all percentages will be presented to one decimal place.
- Individual data listings of all data represented on the eCRF will be provided as an appendix to facilitate investigation of the tabulated values and to allow for the clinical review of all variables. All data listings will be sorted by dose Cohort, site-subject number, visit, and time points where appropriate.
- Post-dose data from unscheduled visits will be excluded from the summary tables but included in the data listings.

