4.4 Handling of missing and incomplete data

Available data at each time point will be presented. The denominator for percentages will be based on the number of subjects in the appropriate treatment or cohort group for summary purposes.

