Table 14.2-8.1	Summary of Score and Change from Baseline in MMES During Double-Blind Therapy / Full Analysis Set
Table 14.2-8.2	Summary of Score and Change from Baseline in MMES During Open-Label Extension Therapy / Full Analysis Set
Table 14.2-8.3	Summary of Score and Change from Baseline in UCEIS During Double-Blind Therapy / Full Analysis Set
Table 14.2-8.4	Summary of Score and Change from Baseline in UCEIS During Open-Label Extension Therapy Period / Full Analysis Set
Table 14.2-8.5	Summary of Score and Change from Baseline in Total Mayo Score During Double-Blind Therapy Period / Full Analysis Set
Table 14.2-8.6	Summary of Score and Change from Baseline in Total Mayo Score During Open-Label Extension Period / Full Analysis Set
Table 14.2-8.7	Summary of Score and Change from Baseline in Partial Mayo Score During Double-Blind Therapy Period and Double-

Forms

Title Statistical Analysis Plan Template

Code	Version	Effective Date	Page
FRM_ST03_032	01	23 Apr 2015	44 of 53

Number	Title
	Blind Therapy Follow-Up Period / Full Analysis Set
Table 14.2-8.8	Summary of Score and Change from Baseline in Partial Mayo Score During Open-Label Extension Therapy Period and Open-Label Extension Therapy Follow-Up Period / Full Analysis Set
Table 14.3.1-1.1	Overall Summary of Treatment-Emergent Adverse Events During Study / Safety Analysis Set
Table 14.3.1-1.2	Summary of Treatment-Emergent Adverse Events During Double-Blind Therapy Period and Double-Blind Therapy Follow-Up Period / Safety Analysis Set
Table 14.3.1-1.3	Summary of Treatment-Emergent Adverse Events During Double-Blind Induction Therapy Period / Safety Analysis Set
Table 14.3.1-1.4	Summary of Treatment-Emergent Adverse Events During Open-Label Extension Therapy Period and Open-Label Extension Therapy Follow-Up Period / Safety Analysis Set
Table 14.3.1-2.1	Treatment-Emergent Adverse Events By System Organ Class and Preferred Term During Double-Blind Therapy Period and Double-Blind Therapy Follow-Up Period / Safety Analysis Set
Table 14.3.1-2.2	Treatment-Emergent Adverse Events By System Organ Class and Preferred Term Double-Blind Induction Therapy Period / Safety Analysis Set
Table 14.3.1-2.3	Treatment-Emergent Adverse Events By System Organ Class and Preferred Term During Open-Label Extension Therapy Period and Open-Label Extension Therapy Follow-Up Period / Safety Analysis Set

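### The pooled double-blind adverse-event tables give crude percentages by dose over scheduled observation of about 12 to 64 weeks, so dose and placebo comparisons in them are confounded with observation time

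*SAP*

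**What the plan says.** **Measure.** SAP 8.1: "TEAE will be summarized in a table that presents the number and percentage of subjects with any TEAE". The sentence goes on to serious, drug-related and discontinuation events and to death, both overall and within the induction, LTE and OLE periods, by dose against placebo. Event totals are added. On percentages, SAP 4.4 says: "The denominator for percentages will be based on the number of subjects in the appropriate treatment or cohort group for summary purposes". Neither document plans a person-time rate or a time-to-first-event summary for adverse events.

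**Window.** The footnotes to SAP Table 2 (Section 4.1) define it: "Double-Blind Therapy Period includes both Double-Blind Induction Therapy Period and LTE Therapy Period" and "Double-Blind Therapy Follow-up Period includes both Follow-up Periods after Double-Blind Therapy Period and LTE Therapy Period". Table 14.3.1-1.2 is titled "Summary of Treatment-Emergent Adverse Events During Double-Blind Therapy Period and Double-Blind Therapy Follow-Up Period / Safety Analysis Set". Tables 14.3.1-2.1, 2.4, 3.1, 4.1 and 5.1 use the same window.

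**Who is observed for how long.** Protocol 8.1.5: "Post-treatment Follow-up assessments will continue for 16 weeks after the last infusion associated with the subject's treatment period". LTE entry required a clinical response or mucosal healing at Week 12 (Protocol 6.1.2), and "The LTE is only active for subjects who entered it prior to approval of Amendment 2". Under Amendment 2, subjects who complete induction can enter the OLE whether or not they responded (Protocol 7.4). LTE subjects who worsen can switch to the OLE up to Week 28 (Protocol 6.1.4).

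**What else is listed.** Each pooled table has an induction-only counterpart (14.3.1-1.3, 2.2, 2.5, 3.2, 4.2, 5.2). SAP 9.4 lists no adverse-event table for the LTE alone.

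**The concern.** A crude percentage with at least one event rises with time observed. Two groups can be compared on it only if their windows match. Here the window depends on Week 12 outcome, on the protocol version in force and on later flare. The first and third may depend on treatment. The second may depend on dose, because cohorts opened in dose order. Placebo subjects from all cohorts are combined (SAP 4.1), so the placebo column also mixes windows.

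Safety and tolerability by dose is the Part A primary objective. A reader of the final report could take a difference in the pooled tables for a dose effect, or miss a real one, when observation time alone produced the pattern. Nothing in the SAP warns of this or says which set of tables should carry the comparison.

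**Working it through.** **1. The plan's own windows reproduce.** Last induction infusion at Week 10 + 16 = Week 26. Last LTE infusion at Week 48 + 16 = Week 64. OLE entrants leave the double-blind window at about Week 12. LTE-to-OLE switchers leave by about Week 28.

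**2. Risk by window.** Assume one constant first-event hazard h at every dose. The documents give no event rate, so h is an assumption and is varied.

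P(event by week w) = 1 − exp(−h·w/52)

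| h per year | 12 weeks | 26 weeks | 64 weeks |
|---|---|---|---|
| 0.5 | 0.109 | 0.221 | 0.460 |
| 1.0 | 0.206 | 0.393 | 0.708 |
| 2.0 | 0.370 | 0.632 | 0.915 |

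**3. One assumed split.** The documents give no counts by cohort.

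- Early cohort: half in the LTE to Week 64, half to Week 26. Mean window 0.5×64 + 0.5×26 = 45 weeks.
- Late cohort: 80% to the OLE at Week 12, 20% to Week 26. Mean window 0.8×12 + 0.2×26 = 14.8 weeks.
- At h = 1.0: 0.5×0.708 + 0.5×0.393 = 55%, against 0.8×0.206 + 0.2×0.393 = 24%.
- At h = 0.5: 34% against 13%. At h = 2.0: 77% against 42%.

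With no LTE entrants at all in the early cohort, h = 1.0 still gives 39% against 24%.

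**4. Direction can reverse.** Suppose both doses ran wholly under the LTE rule and LTE entry was 20% at the lower dose and 60% at the higher, with the rest observed to Week 26. At h = 1.0 the lower dose shows 0.2×0.708 + 0.8×0.393 = 46% and the higher 0.6×0.708 + 0.4×0.393 = 58%.

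**5. Does a rate per subject-year cure it?** Under a constant hazard of 1.0 per year, yes: both cohorts in step 3 show 100 first events per 100 subject-years. Now let the hazard be 1.0 for 12 weeks and zero afterwards. Both cohorts show the same crude 20.6%. Time to first event or end of observation, per subject:

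- First 12 weeks: (1 − exp(−12/52))/1.0 = 0.206 years in both cohorts.
- Early cohort: the event-free 0.794 add on average 0.5×(52/52) + 0.5×(14/52) = 0.635 years, giving 0.206 + 0.794×0.635 = 0.710.
- Late cohort: they add 0.2×(14/52) = 0.054 years, giving 0.206 + 0.794×0.054 = 0.249.
- Rates: 0.206/0.710 = 29, against 0.206/0.249 = 83 per 100 subject-years.

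This is an extreme case, but the rate then creates a difference where the crude percentage shows none.

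**The case against.** The strongest reply is that an equal-window comparison is already planned. Every pooled table has an induction-only counterpart with the same scheduled 12 weeks for all. The adverse-event tables in the Week 12 unblinded package (SAP 9.4.1) are all induction-only. Dose escalation rests on safety reviews at Weeks 4 and 6 (Protocol 6.3). The study is descriptive, with 9 active subjects per Part A cohort. All of this stands and confines the problem to how the pooled tables are read.

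A reader might infer more: that the pooled tables flatter the highest dose. Enrollment began under Amendment 1 and doses ascended, so longer observation in early, low-dose cohorts is plausible. The documents do not establish it:

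- They give no cohort opening dates and no LTE or OLE counts.
- Amendments 1 and 2 are dated 15 Oct 2015 and 04 Oct 2016, and cohorts were projected about 3 months apart, so Cohort 3 could have opened under Amendment 1. Against that, Amendment 2 moved the 3.0 and 10 mg/kg reviews from Week 8 to Week 6, which suggests slower progress.
- Cohort 4 adds 18 active subjects at whichever dose is recommended, so late subjects may sit in any dose column.

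A reader might also infer that an effective drug is penalised against placebo because more responders enter the LTE. LTE entry of 40% against 20% gives 52% against 46% at h = 1.0, but that omits the 12-week cut-off for OLE entrants and so does not model these tables.

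It is also fair to say that SAP 8.1 already promises LTE-period summaries and that shells are in a separate document. The promise is not matched by any title in SAP 9.4.

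**Conclusion.** The point holds for the six pooled tables. Their percentages mix dose with scheduled observation of about 12, 26, up to 28 or 64 weeks, and neither a rate nor a warning is planned. In the illustration the distortion is 55% against 24% with identical true risk (34% against 13% and 77% against 42% at half and double the hazard). Those sizes rest on an assumed constant hazard, an assumed split, LTE subjects all staying to Week 64, and no dropout. Earlier switching or discontinuation would shorten the longer windows.

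The sign is not determined: it can favour either dose, and the placebo comparison is equally open. Escalation decisions and the induction-only tables are not affected, so this is a reporting weakness that should be corrected, not a flaw in the primary safety comparison. The reading of the window rests on the footnotes to SAP Table 2, since the figures that illustrate it are not reproduced in the available text.

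**What to change.** 1. In SAP 8.1, state that the induction-only tables (14.3.1-1.3, 2.2, 2.5, 3.2, 4.2, 5.2) are the basis for between-dose and drug-placebo comparisons of adverse events.
2. In SAP 9.4, list the LTE-period adverse-event summary that SAP 8.1 already promises.
3. In Table 14.3.1-1.2, add subject-years of double-blind observation by dose, counted from first dose to first OLE dose or last double-blind follow-up. For the main categories only, add a supplementary exposure-adjusted incidence (subjects with an event per 100 subject-years to first event). Footnote that observation time differs by cohort and response and that the rate assumes a roughly constant hazard.

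The cost is SAP wording, one more listed summary and modest programming; dose and onset dates are already collected. The downside is the one in step 5: scheduled dosing goes from every 2 weeks to every 4 weeks to none, so a constant hazard is doubtful and the rate misleads if events cluster early. It therefore supplements the induction-only comparison and does not replace it.
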